#### **5.4. Premature Termination of Treatment/Withdrawal of Subjects**

The Investigator must guard the subject's welfare and should discontinue study drug treatment at any time that this action appears to be in the subject's best interest. Subjects may discontinue study drug treatment and may withdraw or be removed from the study at any time. Possible reasons for such actions may include, but are not limited to, the following:

- The occurrence of serious or unexpected unwanted effects attributable to the study drug(s) or study procedure(s)
- In the event of abnormal laboratory results judged to be related to study drug(s) or study procedure(s) and of clinical significance
- Any significant protocol violation (including demonstrated lack of compliance)
- Serious difficulty in obtaining blood samples
- Enrolled subject withdraws consent
- Intercurrent illness requiring medication that might interfere with the study
- Other reasons as determined by the Investigator

It is the right and duty of the Investigator to interrupt the treatment of any study subject whose health or well-being may be threatened by continuation in this study.

Once a study subject has received study drug under this protocol, the subject must be followed for safety as required in the protocol (see [Section 7](#)). In the event that a study subject discontinues treatment prematurely, every effort will be made to document the reason for premature termination and obtain follow-up safety data.

Should the enrollment rate lag or significant numbers of clearly non-eligible and/or non-evaluable subjects be entered in the study, Halozyme may elect to terminate the study at any and all investigational sites. Halozyme also has the right to terminate the study at any time for non-adherence to protocol, unavailability of the Investigator or his or her study staff for Halozyme or its designated monitoring personnel, or for administrative reasons, at any time.

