### Dataset for Analysis

The primary analysis data set for this study will consist of all evaluable subjects. An evaluable subject is one who has completed dosing (or prematurely discontinued the administration due to a toxicity) and has undergone sufficient assessments to allow an assessment of the tolerability of the administration. A secondary analysis data set will consist of all intent-to treat subjects (ITT) (i.e., all subjects enrolled, defined as subjects assigned a subject identification number at the time of study enrollment in anticipation of receiving a dose of study drug). The safety analysis data set is all subjects exposed to rHuPH20 or placebo control.

The hypothesis is that 1) pre-treatment of rHuPH20 prior to nickel allergy testing will decrease the severity of the allergic skin reaction as compared to placebo control and 2) rHuPH20 will decrease the severity of nickel contact dermatitis as compared to control. The null hypothesis for this study is that rHuPH20 will not be different than what will be observed from placebo control. The alternative hypothesis is that rHuPH20 will be better than placebo control.

The sample size of 20 evaluable subjects is intended to provide a sufficient sample size to allow for a meaningful comparison between rHuPH20 and placebo control.

All data collected, including demographics, baseline information, contact dermatitis scoring, safety data, will be summarized by treatment group. Descriptive statistics including the number of observations (N), mean, standard deviation, median, and range will be presented for the continuous variables. Frequency and percentage will be presented for categorical variables. Figures of the individual measurements over time by subject and means by treatment group may also be provided.

Descriptive statistics will be used to summarize all efficacy variables. No formal statistical comparisons between treatments are planned.

All safety data will be examined, including AEs, physical examination findings, and vital signs. The incidence of subjects with AEs will be tabulated by MedDRA System Organ Class (SOC) and Preferred Term, seriousness, severity grade, relatedness to study drug, and localization to infusion site. Descriptive statistics will be used to summarize all safety variables.

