5. ANALYSIS POPULATIONS

The ITT population will include all enrolled subjects (all subjects who got a subject identification number assigned at the time of study enrollment in anticipation of receiving a dose of study drug).

The Safety population will include all subjects who receive at least one dose of study drug.

The Evaluable population will include all evaluable subjects. An evaluable subject is one who has completed dosing (or prematurely discontinued the administration due to a toxicity) and has undergone sufficient assessments to allow an assessment of the tolerability of the administration.

A subject is considered to have undergone sufficient assessments to allow an assessment of the tolerability of the administration if the subject has at least one ICDRG score reported on Day 4 or later.

A subject is considered to have prematurely discontinued the administration due to toxicity if the subject has Adverse Event checked as the reason for not completing the study on the Study Completion/Termination CRF page, and has Drug Withdrawn as the action taken with study drug checked on the Adverse Event CRF page.

Efficacy analyses will be run on the Evaluable population and the ITT (Intent-to-Treat) population. Analyses run on the Evaluable population will be considered the primary analyses.

Safety analyses will be run on the Safety population.

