7. DEMOGRAPHIC AND BASELINE CHARACTERISTICS

Demographic and baseline characteristics variables include: age, sex, ethnicity, race and the concentration of nickel sulfate assigned. Other baseline characteristics include: medical history and hematology and CBC with differential, including incidence rates of clinically significant abnormalities at screening. Demographic and baseline characteristics will be summarized for the Safety, ITT and Evaluable analysis populations.

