Laboratory Parameter	ITT (N=)	Safety (N=)	Evaluable (N=)
WBC (X 1000/uL)			
N	n	n	n
Mean (SD)	xx.x (xx.xx)	xx.x (xx.xx)	xx.x (xx.xx)
Median	xx.x	xx.x	xx.x
Min, Max	xx, xx	xx, xx	xx, xx
RBC (X Mil/uL)			
N	n	n	n
Mean (SD)	xx.x (xx.xx)	xx.x (xx.xx)	xx.x (xx.xx)
Median	xx.x	xx.x	xx.x
Min, Max	xx, xx	xx, xx	xx, xx
..			

path\t_program.sas date time

Programmer note: Table will include the following hematology parameters: Hemoglobin (g/dL), Hematocrit (%), Platelets (X 1000/uL), Neutrophils (segs) (%), Neutrophils (bands) (%), Lymphocytes (%), Monocytes (%), Eosinophils (%) and Basophils (%).

Table
Incidence of Clinically Significant Laboratory Abnormalities at Screening
All Subjects

Any Clinically Significant Abnormalities?	ITT (N=)	Safety (N=)	Evaluable (N=)
WBC	n (%)	n (%)	n (%)
RBC	n (%)	n (%)	n (%)
Hemoglobin	n (%)	n (%)	n (%)
Hematocrit	n (%)	n (%)	n (%)
Platelets	n (%)	n (%)	n (%)
Neutrophils (segs)	n (%)	n (%)	n (%)
Neutrophils (bands)	n (%)	n (%)	n (%)
Lymphocytes	n (%)	n (%)	n (%)
Monocytes	n (%)	n (%)	n (%)
Eosinophils	n (%)	n (%)	n (%)
Basophils	n (%)	n (%)	n (%)

path\t_program.sas date time

Table 6.1
Day of Maximal ICDRG Score
Evaluable Population

Day of ICDRG Maximal Severity Score	Treatment Regimen 2 (N=)	
	rHuPH20	Placebo
Never had an ICDRG Score More Severe than Day 3	n (%)	n (%)
Day 4	n (%)	n (%)
Day 5	n (%)	n (%)
Day 6	n (%)	n (%)
Day 7	n (%)	n (%)
Day 14	n (%)	n (%)

Note: For both injection types (rHuPH20 and Placebo), each subject will contribute one result based on the single most severe patch assessment reported.
path\t_program.sas date time

Programmer Note: Table 6.2 will contain the same information for the ITT population.

Table
Treatment Emergent Adverse Events by System Organ Class
Safety Population

System Organ Class / Preferred Term	Safety Population (N=)	
	Number of Subjects [1]	Number of Events
Subjects Reporting at Least One Adverse Event	n (%)	n
System Organ Class 1	n (%)	n
Preferred Term 1	n (%)	n
Preferred Term 2	n (%)	n
.		
System Organ Class 2	n (%)	n
Preferred Term 1	n (%)	n
Preferred Term 2	n (%)	n

[1] At each level of summation (overall, system organ class, preferred term), subjects reporting more than one adverse event are counted only once.
path\t_program.sas date time

Table
Treatment Emergent Adverse Events by System Organ Class and Severity
Safety Population

System Organ Class / Preferred Term [1]	Safety Population (N=)				
	Mild	Moderate	Severe	Life Threatening	Fatal

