APPENDIX C: LISTING LAYOUTS

**Listing
Subject Disposition**

Subject	ITT[1]	Safety[2]	Evaluable[3]	Replaced[4]	Concentration of Nickel Sulfate Used	First Injection Date	Last Injection Date	Total # of Injection(s)	Complete?	Primary Reason for Not Completing
---------	--------	-----------	--------------	-------------	--------------------------------------	----------------------	---------------------	-------------------------	-----------	-----------------------------------

[1] Intent to Treat (ITT): Enrolled subjects who signed informed consent.

[2] Received at least one dose of study drug.

[3] An evaluable subject is one who has completed dosing (or prematurely discontinued the administration due to a toxicity) and has undergone sufficient assessments to allow an assessment of the tolerability of the administration.

[4] Enrolled subjects but not meeting the criteria of evaluable.

path\t_program.sas date time

**Listing
Inclusion/Exclusion Criteria
Part 1 of 4**

Inclusion Criteria:

1:
2:
3:
4:
5:
6:
7:
8:

Exclusion Criteria:

1:
2:
3:
4:
5:
6:
7:
8:
9:
10:
path\t_program.sas date time

Listing 2(cont.)
Inclusion/Exclusion Criteria
Part 2 of 4: Inclusion Criteria

Subject	Date Informed Consent Signed	Inclusion Criteria							
		1	2	3	4	5	6	7	8

path\t_program.sas date time

Listing 2(cont.)
Inclusion/Exclusion Criteria
Part 3 of 4: Exclusion Criteria

Subject	Date Informed Consent Signed	Exclusion Criteria									
		1	2	3	4	5	6	7	8	9	10

path\t_program.sas date time

Listing 2(cont.)
Inclusion/Exclusion Criteria
Part 4 of 4: Waiver

Subject	Comply with ALL Entry Criteria	Entry Criteria Not Met	Exemption Explanation	Exemption Granted By	Date

path\t_program.sas date time

Listing 3
Demographics

Subject	Date of Birth	Age	Sex	Ethnicity	Race
----------------	----------------------	------------	------------	------------------	-------------

[1] Age is calculated by comparing the date of birth and the informed consent date.
path\t_program.sas date time

Listing 4
Medical History

Subject	Mark if None	MH #	Body System	Description	Diagnosis/Onset	Mark if Ongoing
---------	--------------	------	-------------	-------------	-----------------	-----------------

path\t_program.sas date time

Listing 5
Hematology and CBC with Differential
Part 1 of 2

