					TR 1-1	TR 1-2	TR 1-3	TR 1-4	TR 1-1	TR 1-2	TR 1-3	TR 1-4
									None	None	None	None

path\t_program.sas date time

Listing 14 (cont.)
Study Drug Administration – Treatment Regimen 1
Part 3 of 4: Study Drug Administration

Subject	Visit	Treatment Date	TR 1-1		TR 1-2		TR 1-3		TR 1-4	
			Drug Injected?	Time						
No:reason										

path\t_program.sas date time

Listing 14 (cont.)
Study Drug Administration – Treatment Regimen 1
Part 4 of 4: Physical Examination and Safety Review after Injection

Subject	Visit	Treatment Date	Test Category	Asse. Time	AE #			
					TR 1-1	TR 1-2	TR 1-3	TR 1-4
			Physical Exam. (10 mins. Post) Safety Review (30 mins Post)	None	None	None	None	None

path\t_program.sas date time

Listing 15
Study Drug Administration – Treatment Regimen 2
Part 1 of 4: Physical Examination Prior to Injection

Subject	Visit	Subject Randomized?	Treatment Date	Asse. Time	ICDRG Score				AE #			
					TR 2-5	TR 2-6	TR 2-7	TR 2-8	TR 2-5	TR 2-6	TR 2-7	TR 2-8
									None	None	None	None

path\t_program.sas date time

Listing 15 (cont.)
Study Drug Administration – Treatment Regimen 2
Part 2 of 4: Study Drug Administration

Subject	Visit	Treatment Date	TR 2-5		TR 2-6		TR 2-7		TR 2-8	
			Drug Injected?	Time						
No:reason										

path\t_program.sas date time

Listing 15 (cont.)
Study Drug Administration – Treatment Regimen 2
Part 3 of 4: Physical Examination and Safety Review after Injection

Subject	Visit	Treatment Date	Test Category	Asse. Time	AE #			
					TR 2-5	TR 2-6	TR 2-7	TR 2-8
			Physical Exam. (10 mins. Post) Safety Review (30 mins Post)		None	None	None	None

path\t_program.sas date time

Listing 15 (cont.)
Study Drug Administration – Treatment Regimen 2
Part 4 of 4: Application of Nickel Sulfate Patches

Subject	Visit	Treatment Date	Application Time	Mark if Not Done	4 Patches	Not applied Reason	Concentrations of Nickel Sulfate
---------	-------	----------------	------------------	------------------	-----------	--------------------	----------------------------------

path\t_program.sas date time

Listing 16
Adverse Events

Subject	Mark if None	AE Term	Start Date/Time	Resolved Date/Time	Serious	Severity (CTCAE3)	Action Taken with Study Drug	Relationship to Study Drug	Other Action Taken	Outcome
---------	--------------	---------	-----------------	--------------------	---------	-------------------	------------------------------	----------------------------	--------------------	---------

path\t_program.sas date time

Listing 17

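### The SAP's rule for a toxicity stop adds a study non-completion condition that the protocol does not have, so a toxicity stopper recorded as completing the study would drop out of the primary Evaluable set

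*SAP*

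**What the plan says.** Protocol Section 8 (Dataset for Analysis) makes the evaluable subjects the primary analysis set: "An evaluable subject is one who has completed dosing (or prematurely discontinued the administration due to a toxicity"), and who also has enough assessments to judge tolerability. Sections 3.3 and 5.2 give the same definition. None of the three sets a condition on how study completion is recorded.

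SAP Section 5 repeats the definition, declares the Evaluable analyses primary, and then gives two working rules. Assessments are sufficient if there is at least one ICDRG score on Day 4 or later. Administration counts as stopped for toxicity when a participant "has Adverse Event checked as the reason for not completing the study on the Study Completion/Termination CRF page, and has Drug Withdrawn"; the second of these boxes sits on the Adverse Event page and records what was done with study drug. No other route to a toxicity stop is given.

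Protocol Section 5.4 treats stopping drug and leaving the study as different events: "Subjects may discontinue study drug treatment and may withdraw or be removed from the study at any time". It also says that when a subject "discontinues treatment prematurely, every effort will be made to document the reason for premature termination and obtain follow-up safety data".

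**The concern.** The SAP condition replaces an event in dosing with an event in disposition. A subject who stops injections for toxicity and then does what Section 5.4 asks, staying under follow-up to Day 14, may be recorded as completing the study. She then has no reason for non-completion to check and cannot meet the rule. A subject with the same toxicity who leaves the study after a Day 4 score, coded Adverse Event, does meet it. Among toxicity stoppers, fuller follow-up can therefore cost membership of the primary set.

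The subjects at risk are the ones the protocol chose to keep. Losing them would be selective, and membership would turn on a completion code instead of on why dosing stopped.

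**Working it through.** **Where the rules differ.** Take a subject who stopped injections for toxicity, has Drug Withdrawn checked, and has an ICDRG score on Day 4 or later.

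| Disposition record | Protocol | SAP rule read literally |
|---|---|---|
| Completed study | Evaluable | Not Evaluable |
| Not completed, Adverse Event | Evaluable | Evaluable |
| Not completed, another primary reason | Evaluable | Not Evaluable |

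**Can the first row occur?** Protocol Section 5.4 requires safety follow-up of every dosed subject. Section 7.7.2 takes follow-up to Visit 8 unless the subject is withdrawn earlier. SAP Section 10.1 lists stopping study drug and leaving the study as alternatives. Protocol Section 5.2 gives the evaluability definition under a heading on replacement and completion criteria, so such a subject appears to meet those criteria. SAP Listing 1 has a completion field and "Primary Reason for Not Completing", but nothing says whether someone who stops dosing and attends Day 14 is a completer.

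**Can the Day 4 requirement be met?** Planned injections are 4 on Day 1 (Regimen 2) and 8 on each of Days 3 to 7 (4 sites × 2 regimens): 4 + 5 × 8 = 44. I assume that completing dosing means all 44, since the documents do not define it.

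| Last injection day | Injections given | Share of 44 |
|---|---|---|
| Day 3 | 4 + 8 = 12 | 27% |
| Day 4 | 12 + 8 = 20 | 45% |
| Day 5 | 20 + 8 = 28 | 64% |
| Day 6 | 28 + 8 = 36 | 82% |

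None of these subjects has completed dosing, so each depends on the toxicity route. Protocol Appendix A schedules test area assessment on Days 3 to 7 and Day 14, so a score on Day 4 or later is possible in every row.

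**Which outputs change.** Among efficacy tables, only Table 6.1 (day of maximal score, Regimen 2), where "each subject will contribute one result based on the single most severe patch assessment reported" for each injection type. The Evaluable and replaced counts in Table 1 also change, as do the Evaluable columns of Tables 2 to 5; Section 7 says "Demographic and baseline characteristics will be summarized for the Safety, ITT and Evaluable analysis populations". Table 6.2 (ITT) and the safety tables keep her. Figure 1 and Listing 8, which carry the qualitative ICDRG review, show no Evaluable restriction.

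**Size in Table 6.1.** Let a cell hold k of N subjects and remove m.

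- If all m were in the cell, it goes from k/N to (k − m)/(N − m). The largest change is at k = m, from m/N to 0.
- If none were in it, it goes from k/N to k/(N − m), a rise of km/[N(N − m)]. This is largest at k = N − m, where it equals m/N.

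The maximum shift is therefore m/N. The documents give no figure for m, so I assume 0, 1 or 2. N runs from the planned 20 evaluable to the maximum enrolment of 30.

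| m | N = 20 | N = 30 |
|---|---|---|
| 0 | 0 | 0 |
| 1 | 5.0 points | 3.3 points |
| 2 | 10.0 points | 6.7 points |

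A more typical cell moves less. With k = 5, N = 20 and m = 1, 25.0% becomes 4/19 = 21.1% if she was in the cell, or 5/19 = 26.3% if she was not.

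**The case against.** The strongest point is that the Study Completion/Termination page is not in the documents. Table 1 and Listing 1 show a single disposition record with one primary reason, and Adverse Event is among the options. No separate record of treatment discontinuation appears in the list of listings. Sites may well have coded every toxicity stopper as not completing because of an adverse event, and then the two definitions agree. This stands, and it is why the conclusion is conditional.

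Second, the SAP says if, not only if, so its rule could be read as sufficient without excluding anyone else. That is fair as grammar. But it is the only working rule given, and SAP Section 4 has programs checked for consistency with the plan, so a programmer would apply it as the definition.

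Third, ICDRG scores are captured on the study drug administration pages, under the examination before injection, and Section 5.4 promises safety follow-up without mentioning efficacy scoring. A subject whose last injection was on Day 3 might have no later score and would fail the Day 4 requirement anyway. That limits the concern for the earliest stoppers. It does not remove it: Day 14 scoring is scheduled, and a subject last injected on Day 4, 5 or 6 should already have a pre-injection score from Day 4.

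Fourth, requiring two pages to agree is a legitimate cross-check that an adverse event ended dosing. The cross-check is reasonable, but study completion is the wrong field for it, and the dosing record can serve instead.

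Finally, the effect is small and both within-subject arms leave together. Both are true and set the severity. Removing both arms does not prevent the selective loss of subjects who stopped for toxicity.

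**Conclusion.** The concern holds and is minor. As written, SAP Section 5 sets a condition on study completion that neither the protocol nor the SAP's own definition contains, and it can exclude a toxicity stopper whom the protocol counts as evaluable. Each such subject shifts a Table 6.1 cell by at most 5.0 points at N = 20, and usually by less. There is no effect on any test, because none is planned.

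This rests on two assumptions: that the Section 5 rule is applied as the full definition, and that at least one toxicity stopper is recorded as completing the study. How often the second occurs cannot be told from the documents, so confidence is medium.

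**What to change.** Before database lock and unblinding, rewrite the toxicity sentence in SAP Section 5 so that a stop is identified from Drug Withdrawn as the action taken with study drug on the Adverse Event page, without the study-completion condition. Keep the requirement for an ICDRG score on Day 4 or later.

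This also keeps a subject whose disposition page gives another primary reason. Check those cases, still blinded, against the dosing record in Listings 14 and 15 (the "Drug Injected" field and the reason given when the answer is no), and state in the SAP that this record settles a disagreement.

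Footnote [4] of Table 1 and Listing 1 can stay. It follows the protocol's rule that non-evaluable subjects are replaced, and it comes right once Section 5 does.

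The cost is an edit to one SAP rule, one derivation and a short blinded check of any discordant cases. The fields are already collected (Adverse Events, plate 97; study drug administration, plates 12 to 16). After unblinding, SAP Section 4 would make the same change post hoc.

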6. SUBJECT DISPOSITION

Subject disposition information will be summarized for all subjects. Summaries will include: the number of subjects in each analysis (ITT, Safety, Evaluable) population, the number of subjects replaced, the number of subjects completing the study and the primary reason for discontinuation.

7. DEMOGRAPHIC AND BASELINE CHARACTERISTICS

Demographic and baseline characteristics variables include: age, sex, ethnicity, race and the concentration of nickel sulfate assigned. Other baseline characteristics include: medical history and hematology and CBC with differential, including incidence rates of clinically significant abnormalities at screening. Demographic and baseline characteristics will be summarized for the Safety, ITT and Evaluable analysis populations.

8. EFFICACY ANALYSES

Efficacy analyses will be carried out on both the Evaluable and the ITT analysis populations.

8.1 Primary Variables

The primary efficacy endpoint will be based on the International Contact Dermatitis Research Group (ICDRG) Scoring Scale. Using the ICDRG Scoring Scale, each score will be assigned a Sponsor-defined “grade”. Scores with stronger reactions will be assigned grades with higher values with a maximum grade of 3; scores with weaker reactions will receive lower values with a minimum grade of 0. Grade assignments based on the ICDRG Scoring Scale are shown in the table below.

International Contact Dermatitis Research Group (ICDRG) Scoring Scale

Grade	Score	Interpretation
0	-	Negative reaction
1/2	?	Doubtful reaction; faint macular erythema only
1	+	Weak (nonvesicular) positive reaction; erythema, infiltration, papules, vesicles
2	++	Strong (vesicular) positive reaction; erythema, infiltration, papules, vesicles
3	+++	Extreme positive reaction; bullous reaction
NA	IR	Irritant reaction of different types

Treatment effect of rHuPH20 or placebo control injection on the exposure to topical nickel allergen will be assessed using ICDRG grades for Treatment Regimens 1 and 2 at Day 3 through Day 7 and Day 14.

Regimen 2 only: For each subject, the day of maximal ICDRG score will be determined for each injection type (rHuPH20 and Placebo). The maximal ICDRG score will be the highest score reported for each subject. If the maximal ICDRG score for a particular subject is reported more than one time, the first instance will be used to determine the day when the maximal ICDRG score was reached.

